## Protocol

86 healthy subjects took part in the study (61 females), with a mean age of 52.8 (SD=17.0, range 25-85) and a mean of 14.0 years of education (SD= 5.2, range 3-31). The distribution of demographic data is shown in Table 2. Subjects with past or present neurological or psychiatric diseases were excluded from the study, as well as subjects with visual disturbances. The presence of myopia or astigmatism did not represent an exclusion criteria if they were corrected by the use of glasses. All participants took part in the study on a voluntary basis after having provided their written informed consent and without receiving any reward. Each VST was administered twice to each participant, with an interval of two weeks, in order to analyze the test-retest effect.

The Visual Scanning Test (VST) involved a visual search for a target between similar visual distractors, projected in the far space. The VST required the presence of a blank wall and a projector and, to be carried out, participants must be positioned in a manner to reproduce a visual field of 52° x 45 °.

Overall, the VST is composed by four trials of 20 cases, each made up by 20 stimuli (see fig 1). On about the 80% of cases, the test provided the presence of target in the left, center or in right hemispace. In the remaining 20% of cases, the test provided the presence of a catch trial ("CT", absence of the target), to assess the presence of frontal disturbances or malingering. The test is constructed according to an increasing attentional load for the target on the left-hemispace.

Firstly, participants were required to look at a fixation point to always ensure the same starting position. After the start provided by the experimenter, participants were required to actively and free explore the visual field to search for the visual target. During the visual search, they were instructed to detect the presence of a target and naming its identification (saying YES or NO). Two types of errors could be made:

- Saying "NO" during the visual search in cases where the target was present;
- Saying "YES" during the visual search in the CT condition.

The experimenter recorded the reaction times (RTs) from the beginning of the visual search until participant's answer and the accuracy (HITs), through a dedicated response form. Specifically, the experimenter was required to draw a sign in case of error.

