From the recorded data it may be possible to obtain several indexes, mainly related to the reaction times and to the accuracy on VST.

Indexes for *reaction times* (RTs) were related to :

- The total VST RTs (**RTs Total**)
- mean visual searching time for left hemispace (**RTs left**);
- mean visual searching time for right hemispace (**RTs right**)
- the time between the presentation of the visual field and the wrong non-identification of the target (answer "NO", where the target exists, **RT misses**);

- *Catch trials* RTs, that is the time between the presentation of the visual field and the wrong identification of the target (answer “YES”, where the target doesn’t exist, **CT- RTs**);
- The time between the presentation of the visual field and the identification of targets in the left hemisphere in Trial A (**RTs Trial A left**);
- The time between the presentation of the visual field and the identification of targets in the right hemisphere in Trial A (**RTs Trial A right**);
- The changes from mean RTs in trial A to mean RTs in trial D for left hemisphere, which reflect and implicit learning of target position to the left (i.e. Learning index, **LEI left**);
- The changes from mean RTs in trial A to mean RTs in trial D for right hemisphere, which reflect and implicit learning of target position to the right (i.e. Learning index, **LEI right**);
- Space Asymmetry index due to time (**SAI Time**), where RT total represents the RTs average value over the four trials.

Indexes for *accuracy* (HITs) were:

- The total VST HITs (**HITs Total**);
- The accuracy for left hemisphere (**HITs left**);
- The accuracy for right hemisphere (**HITs right**)
- The number of non-existing targets identified (answer “YES”, where the target doesn’t exist, **CT- HITs**);
- Space Asymmetry index due to accuracy (**SAI HITs**), where HITs total represents the accuracy average value over the four trials.

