### Statistical analysis Plan

Data were analyzed using SPSS version 25 (SPSS Inc., Chicago, IL, USA). A multiple linear regression model was first applied to test the independent effects of age, sex, and education on the above mentioned indexes. The best fitting linear model for each index was sought to adjust original scores according to the demographic variables found to be associated with each index ( $p<0.05$ ). The effect of education level was explored after logarithmic, quadratic and reciprocal transformation, while age was included in the models after logarithmic transformation: “ $\log(100\text{-age})$ ”, as suggested by Capitani et al [1]. Corrected scores were calculated by adding (or subtracting) the contribution of each variable for each age group (25-45, 46-65, 66-85) and/or education level ( $\leq 5$  years, 6-13 years,  $\geq 14$  years) [2]. Based on the obtained results, correction grids were created. No adjustment was made to the top end of the scale, to avoid errors due to the fixed upper limit of the test scores. Adjusted scores were then ranked, and by means of a non-parametric procedure [3] tolerance limits (both outer and inner one-sided) were defined. Above the outer tolerance limit, it is expected to find at least 95% of the normal population (with 95% confidence), while above the inner tolerance limit, it is expected to find at most 95% of the population (with 95% confidence). The scores falling between the outer and inner tolerance limits are defined “borderline scores” because a controlled judgment cannot be expressed. Given our sample size, outer and inner tolerance limits were fixed, respectively, based on the values of the first and ninth ranked scores, after demographic adjustments. Finally, after having tested the adjusted scores for normality, differences between LEI left and LEI right, CT HITs and HITs total, and RTs trial A left and RTs trial A right, were evaluated by using a paired t-test or a Wilcoxon Signed Ranks Test, accordingly. A significant level of  $p<0.05$  was used in all tests. CT-RTs, RTs total and RT misses values were compared by using a repeated measures ANOVA followed by Bonferroni’s multiple comparison tests, if the ANOVA test showed significance ( $p<0.05$ ).

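### CT-HITs, defined as a count of false YES answers, is tested against HITs total, an accuracy score, so a significant result would not show that catch-trial and target accuracy differ

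*Combined protocol and SAP*

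**What the plan says.** The Protocol describes four trials of 20 cases. About 80% of cases contain a target; for the rest, "In the remaining 20% of cases, the test provided the presence of a catch trial". It states that "Two types of errors could be made": answering NO when a target is there, and answering YES "during the visual search in the CT condition". The experimenter records reaction times "and the accuracy (HITs), through a dedicated response form", so HITs denotes accuracy.

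The index list that follows places CT-HITs under accuracy but defines it as "The number of non-existing targets identified". HITs total is listed as "The total VST HITs". In the entry for the asymmetry index SAI HITs, "HITs total represents the accuracy average value over the four trials". The list does not say whether catch cases count towards HITs total.

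The Statistical analysis Plan then evaluates "differences between LEI left and LEI right, CT HITs and HITs total, and RTs trial A left and RTs trial A right" by a paired t-test or a Wilcoxon signed ranks test at p<0.05, on demographically adjusted scores. It gives no hypothesis for the CT HITs and HITs total pair. Apart from the demographic adjustment, it describes no transformation of either score.

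**The concern.** A paired test of a difference is informative when zero difference means something. Here one score rises as performance worsens and the other rises as it improves, and they may also be on different scales. Healthy participants who are equally accurate on both case types would have a low CT-HITs and a high HITs total, and the test would call that a difference.

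The likely purpose is to see whether people are as accurate at rejecting absent targets as at finding present ones. That purpose is inferred, since the plan states none. If it is right, a reported p<0.05 invites the conclusion that catch-trial and target accuracy differ when the data need show nothing of the kind.

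**Working it through.** **Inputs.** From the Protocol: 4 x 20 = 80 cases; 20% of 80 = 16 catch cases and 80% = 64 target cases (the split is given as approximate); n = 86. From the Statistical analysis Plan: alpha 0.05, taken as two-sided. The documents give no error rates, so these are assumptions. They also give no power or effect size for this comparison, so there is no stated figure to reproduce.

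**What the null hypothesis means.** Let the error rate be e on both case types, which is equal accuracy. Expected CT-HITs is then 16e. The means coincide only where:

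| Reading of HITs total | Condition for equal means | Solution |
|---|---|---|
| Sum, target cases only | 64(1-e) = 16e | e = 64/80 = 80% |
| Sum, all cases | 80(1-e) = 16e | e = 80/96 = 83% |
| Per-trial average, target cases only | 16(1-e) = 16e | e = 50% |
| Per-trial average, all cases | 20(1-e) = 16e | e = 20/36 = 56% |
| Both scores as proportions | 1-e = e | e = 50% |

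For example, at e = 5% CT-HITs averages 16 x 0.05 = 0.8. HITs total averages 64 x 0.95 = 60.8 as a sum over target cases, or 60.8/4 = 15.2 per trial. As proportions the comparison is 0.05 against 0.95. Accuracy is identical in every case, yet the scores are far apart.

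**Rejection rate at equal accuracy.** Hits were simulated as Bin(64, 1-e) and false YES answers as Bin(16, e), with 86 independent participants and unadjusted scores. For every reading in the table the paired t-test rejects in 100% of runs at each error rate tried from 1% to 40%.

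**If correct rejections were scored instead.** The catch score becomes 16 minus the false YES count.
- Against a sum of 64 or 80, or against a per-trial average over all 20 cases, the t-test still rejects in 100% of runs at equal accuracy.
- Against a per-trial average over target cases only, both scores run from 0 to 16 and the test is valid. This needs exactly 16 catch cases. With 12 or 20 it rejects in 100% of runs at 5% error.

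**Corrected comparison.** The difference tested is hits/64 - (1 - false YES/16).
- At equal accuracy with 1-40% error, the t-test rejects in about 4-6% of runs. The Wilcoxon test is somewhat higher near ceiling: 14.5% at 1% error and about 6-9% at 2-10%.
- With 5% error on target cases and 7% on catch cases, the t-test rejects in about 77% of runs. With 5% against 8% it rejects in about 98%.

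**The case against.** **CT-HITs may be misworded.** It sits under the accuracy indexes, and HITs means accuracy elsewhere, so correct rejections may have been scored. This is plausible and would remove the direction fault. It would not make the test valid in general, because the scale must also match. It does so on one natural reading: the target-only per-trial average with exactly 16 catch cases. A reader might therefore infer too much from the claim that no reading can work. That claim holds only for CT-HITs as literally defined.

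**The hypothesis is inferred.** If both scores are proportions and HITs total covers target cases only, the literal test compares the hit rate with the false-alarm rate. That is a coherent check that participants discriminate, and the Protocol does use catch trials to look for frontal disturbances or malingering. This stands, but in healthy participants the check is passed almost by default. It does not rescue the sum or raw-count readings.

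**The unit of HITs total may be less unsettled than it looks.** The average wording appears only in the SAI HITs entry, beside a formula probably lost when the text was extracted, and it may apply to that index alone. This stands. Whether catch cases count is still not stated.

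**A reader might infer that the test would also miss real differences.** That can be shown for a 0-1 proportion against a raw count. With 20% target error and 5% catch error the means coincide (1 - 0.20 = 16 x 0.05 = 0.80), and the t-test rejects in only about 5% of runs. No section states that pairing, and the example needs exactly 16 catch cases. With 12 or 20 catch cases, rejection is about 66% or 47%. It should not be presented as the expected behaviour of the plan.

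**Conclusion.** The point holds as a fault in the comparison as written: a count of errors is tested against an accuracy score with no reversal or common scale. On the sum, per-trial-average and both-as-proportions readings, rejection at equal accuracy is 100% in simulation, against about 4-6% for a properly aligned t-test. A significant result would show at most that participants discriminate target from no target.

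This rests on the literal definition of CT-HITs, a 64/16 split, assumed error rates, independent answers and unadjusted scores. The exact split matters little to the main result: with 12 or 20 catch cases the literal sum and both-as-proportions comparisons still reject in 100% of runs at the error rates tried between 1% and 40%.

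A reader might infer that the normative cut-offs are undermined. The documents do not support that from this comparison, which sets no correction grid and no tolerance limit. It is one secondary test, worth correcting because its p-value is easily misread.

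**What to change.** For this comparison, define for each participant:

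- catch-trial accuracy = 1 - (false YES answers / number of catch cases);
- target accuracy = hits / number of target-present cases, with catch cases excluded.

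Test the within-participant difference between the two. Reword the CT-HITs entry so that it says whether false YES answers or correct rejections are counted. Give HITs total one unit and denominator, stating whether catch cases are included. Add a sentence giving the hypothesis that the comparison addresses. If a check of discrimination was intended, say so and report it as the hit rate against the false-alarm rate.

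The cost is two definitions, one sentence and one recomputed test. Errors were marked on the response form, so no new data should be needed. The downside is that a result almost certain to be significant as now defined may no longer be so.

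### RTs total is a poor comparator for the two error times: on the plain reading it averages all cases, including correct NO answers on catch trials, so case mix alone can produce a difference

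*Combined protocol and SAP*

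**What the plan says.** The last sentence of the Statistical analysis Plan puts three time indexes into one within-subject comparison: "CT-RTs, RTs total and RT misses values were compared by using a repeated measures ANOVA". Bonferroni comparisons follow if the ANOVA is significant at 0.05.

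The Protocol's list of reaction-time indexes defines them as follows:

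- **RT misses** is "the time between the presentation of the visual field and the wrong non-identification of the target", that is, a NO when a target is present.
- **CT-RTs** is the time to a wrong YES when no target is present.
- **RTs Total** is given only as "The total VST RTs". Under the time asymmetry index the text adds "where RT total represents the RTs average value over the four trials".

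On which cases produce a time, the Protocol says "The experimenter recorded the reaction times (RTs) from the beginning of the visual search until participant's answer", with no limit to correct answers. On the make-up of the test, it says "the VST is composed by four trials of 20 cases", and also "In the remaining 20% of cases, the test provided the presence of a catch trial". The two Trial A indexes, by contrast, are expressly tied to identified targets. The plan defines no time index for correct NO answers on catch cases, and none for correct YES answers over the whole test.

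**The concern.** Two of the ANOVA levels are times on one kind of error each. The third appears to be an average over everything: correct YES answers (hits), both kinds of error, and correct NO answers on catch cases (correct rejections). Correct rejections belong to neither error index, yet they carry nearly a fifth of the weight in RTs total.

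If correct rejections differ in duration from hits, RTs total moves away from the hit time for a reason unrelated to errors. Suppose they are slower. False YES answers that take exactly as long as hits would then look fast against RTs total, and a real slowing on misses would look smaller than it is. If they are quicker, both distortions reverse. A significant pairwise result could not be attributed to the errors themselves.

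**Working it through.** The plan gives no effect size or power figure for this ANOVA, so there is nothing of its own to reproduce.

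**Inputs from the documents.** There are 4 × 20 = 80 cases. About 20% are catch cases, 0.20 × 80 = 16, which leaves about 64 with a target. There are 86 subjects. The ANOVA level is 0.05, and three pairwise tests under Bonferroni give 0.05/3 each.

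**Assumed inputs.** Per subject: 60 hits, 4 misses (60 + 4 = 64), 2 false YES and 14 correct rejections (2 + 14 = 16). Hits, misses and false YES all have mean time 1. Correct rejections have mean time r, with r from 1 to 2.

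**Step 1: shift in RTs total.** RTs total = (60 + 4 + 2 + 14r)/80 = (66 + 14r)/80. The weight on correct rejections is 14/80 = 17.5%.

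| r | RTs total | Above hit time | Apparent speed-up of false YES (1 − 1/RTs total) |
|---|---|---|---|
| 1 | 80/80 = 1.000 | 0% | 0% |
| 1.25 | 83.5/80 = 1.044 | 4.4% | 4% |
| 1.5 | 87/80 = 1.0875 | 8.75% | 8% |
| 2 | 94/80 = 1.175 | 17.5% | 15% |

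If correct rejections were quicker, say r = 0.75, RTs total would be 76.5/80 = 0.956, and false YES would look slower instead. With 1 to 6 misses and 1 to 2 false YES, the shift is 4.4–4.7%, 8.8–9.4% and 17.5–18.8% at r = 1.25, 1.5 and 2.

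**Step 2: role of the shared errors.** Write T for RTs total, M for the miss time and w for the share of misses. Then T − M = (1 − w) × (mean of all other cases − M). With 4 misses the factor is 1 − 4/80 = 0.95; from 1 to 6 misses it runs from 0.99 to 0.93. The overlap shrinks a difference slightly and cannot create one. The shift in Step 1 comes entirely from the correct rejections.

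**Step 3: masking of a true effect.** Let misses take 1.2 times the hit time. At r = 1.5, T = (60 + 4.8 + 2 + 21)/80 = 1.0975 and 1.2/1.0975 = 1.093, so a 20% slowing shows as 9%. At r = 2, T = 94.8/80 = 1.185 and 1.2/1.185 = 1.013, so it shows as 1%.

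**Step 4: rejection rates with no true difference between false YES and hits.** Simulated paired t-test of the false-YES mean against RTs total at 0.05/3, assuming a case-level CV of 0.5 and a between-subject CV of 0.3:

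| r | n = 86 | n = 40 |
|---|---|---|
| 1 | 2% | 2% |
| 1.25 | 13% | 8% |
| 1.5 | 44% | 24% |
| 2 | 96% | 69% |

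Against the hit time instead of RTs total, the rate stays near 2% throughout. These figures are approximate and ignore the preceding ANOVA gate. For the omnibus F test at 0.05 under another set of assumptions (case-level CV 0.4, 5% misses, 10% false YES, at least one of each error per subject), the rates at n = 86 are 5.9%, 18.8%, 74.8% and 100% at the same four ratios.

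**Step 5: how many subjects contribute.** A complete three-level row needs both error types. With independent errors, the expected number is 86 × (1 − (1 − f)^16) × (1 − (1 − m)^64), where f and m are the false-YES and miss rates. At f = 2/16 and m = 4/64 this is about 75; at 5% and 3%, about 41; at 2% and 1%, about 11. With all 86 subjects but only one error of each type, the rejection rate at r = 1.5 falls from 44% to 28%.

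**The case against.** **The composition of RTs total is inferred.** The documents never list the cases that enter it. That stands. A reader might take it as established that RTs total contains both error types and the correct rejections; the text supports this only as the plain reading. If the sponsor meant something narrower, the plan has to say so.

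**Part against whole.** A reader might infer that comparing two parts with a whole containing them biases the test in itself. Step 2 shows that it does not.

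**Slower correct rejections are assumed.** That also stands. It is plausible that a NO follows a fuller search than a YES, but no text says so, and at a ratio of 1 there is no distortion. The 44% and 96% figures are at the favourable end: they need every healthy subject to have made both kinds of error.

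**The purpose of the ANOVA is not stated.** The documents do not say that it asks whether errors are faster or slower than correct detections, and they do not interpret fast false YES answers as impulsive responding. Neither reading can be attributed to the plan.

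**Correct YES as the single comparator is not a full remedy.** It would set false YES on target-absent displays against correct YES on target-present ones. A miss is also a NO answer, so if NO answers are slow in general, misses will differ from hits for that reason. Hence the contrasts should stay within display type. Even there an error and a correct answer differ in the word spoken, which is inherent in a yes/no task and should be acknowledged when the result is interpreted.

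**Total versus average.** The label and the later description differ, but the average is stated, so this is only a wording ambiguity.

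**Conclusion.** The concern holds in a limited form. Followed as written, and on the plain reading of RTs total, the comparison can yield a difference that reflects the mix of cases and not the timing of errors. Under the assumed counts the shift in RTs total runs from 0% to 17.5% of the hit time as the rejection/hit ratio goes from 1 to 2. The chance of a spurious pairwise rejection runs from about 2% to 96% with all 86 subjects contributing, and is lower with fewer. Which point in that range applies cannot be settled from the documents.

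They do not support the stronger conclusion that the result will be spurious. The defect is nevertheless more than a missing definition, because the plan has no index that would separate an error effect from a case-mix effect. It should be corrected, but it touches only this closing comparison: the demographic correction grids and the tolerance limits do not depend on it.

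**What to change.** Do not use RTs total as a level of this comparison. Replace the ANOVA with two paired contrasts of disjoint mean times per case:

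1. Within target-present cases: misses versus correct YES answers.
2. Within catch cases: false YES versus correct NO answers.

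Apply Bonferroni across the two (0.05/2 = 0.025 each) and report how many subjects contribute to each. State in the index list which cases enter RTs total and that it is an average, and keep it as a normative or descriptive index.

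The cost is small. No new data are needed provided times were kept by case, which RT misses and CT-RTs already require. Two contrasts replace one ANOVA, and only subjects who made the relevant error contribute to each. A subject with just one type of error can still enter one contrast, whereas a complete three-level row needs both.

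### Bonferroni tests conditional on a significant ANOVA are valid but needlessly conservative; ungated Holm declares every pair the plan would, and sometimes more, at the same 5%

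*Combined protocol and SAP*

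**What the plan says.** The last sentence of the Statistical analysis Plan covers this comparison: "CT-RTs, RTs total and RT misses values were compared by using a repeated measures ANOVA". Bonferroni pairwise tests follow only conditionally: "if the ANOVA test showed significance", with 0.05 as the threshold for the ANOVA. The section gives no reason for using both steps, no sphericity check or correction, no power statement, and no primary or confirmatory status for this comparison.

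The Protocol section gives the sample: "86 healthy subjects took part in the study". It defines two of the three measures on wrong answers only. RT misses is "the time between the presentation of the visual field and the wrong non-identification of the target", and CT-RTs is described by the words "that is the time between the presentation of the visual field and the wrong identification of the target". The number of subjects with values on all three measures is not stated.

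**The concern.** Three measures give three pairs. A Bonferroni adjustment over three pairs controls the family-wise error by itself. Requiring a significant ANOVA first can remove a pair from the list of findings but can never add one. Single-step Bonferroni is also not the best available use of the 5%: Holm's step-down procedure uses the same pairwise p-values and is never less powerful. The plan therefore has two avoidable sources of conservatism.

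What is at stake is modest: some true differences between the three measures may go undeclared. The loss matters more if few subjects have all three values. That is possible, because a subject who makes no error of one kind has no reaction time for it and would normally drop out of a repeated measures ANOVA.

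**Working it through.** **Inputs from the documents.** Three within-subject measures, hence 3 pairs; ANOVA threshold 0.05; pairwise tests only if the ANOVA is significant (Statistical analysis Plan). 86 subjects; four trials of 20 cases, so 4 × 20 = 80 cases, of which about 20%, or 0.20 × 80 = 16, are catch trials (Protocol).

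**Assumptions, because the documents give no figures.** Normal data, correlation 0.5, equal SDs unless stated, one measure shifted, two-sided tests. Pairwise tests are paired t-tests, since the plan does not name the pairwise statistic. The n with all three values is taken as 20, 30, 40 or 86. The plan states no power figure for this comparison, so there is none to reproduce.

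**Step 1. Is the gate needed for error control?** The Bonferroni level per pair is 0.05/3 = 0.0167. Family-wise error is at most 3 × 0.0167 = 0.05. If the tests were independent it would be 1 − (1 − 0.0167)³ = 0.049. Simulated at correlation 0.5 and n=86 with no true differences, it is 4.4% without the gate and 3.9% with it. The gate lowers an error rate that is already below 5%.

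**Step 2. Does Holm lose anything the plan would find?** Holm compares the smallest p-value with 0.05/3, the next with 0.05/2 and the last with 0.05, stopping at the first failure. Any pair the plan declares has p < 0.05/3. Every pair with a smaller p-value is then also below 0.05/3, so Holm cannot stop before reaching it. Every pair the plan declares is therefore declared by Holm. In 80,000 simulated data sets there was no exception.

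**Step 3. How much power, and from which step?** Power per truly different pair, one measure shifted by 0.5 SD, 40,000 data sets per setting:

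| n | Plan | Bonferroni, no gate | Holm, no gate | From dropping gate | From Holm | Total |
|---|---|---|---|---|---|---|
| 20 | 36.4% | 37.5% | 40.4% | 1.1 | 2.9 | 4.0 |
| 30 | 57.8% | 58.4% | 62.0% | 0.6 | 3.6 | 4.2 |
| 40 | 73.7% | 74.1% | 77.4% | 0.4 | 3.3 | 3.7 |
| 86 | 98.5% | 98.5% | 99.0% | 0.0 | 0.5 | 0.5 |

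The last three columns are differences in percentage points. Repeat runs differ by up to about a point; Holm at n=20 came out between 40% and 41%.

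At n=86 a 0.5 SD shift is found almost always, so a smaller one is more informative. With a 0.30 SD shift, power per pair is 62.7% under the plan and 66.5% with ungated Holm: 66.5 − 62.7 = 3.8 points. Ungated Bonferroni gives 63.2%, so the gate accounts for about 0.4 of those points.

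**Step 4. Is there a safe version that keeps the gate?** With three conditions, an ANOVA gate followed by unadjusted tests at 0.05 is a closed test, and it looks attractive: 73.9% per pair at n=86 and 0.30 SD. It holds 5% only if the ANOVA itself does. With assumed SDs of 1:1:3 and no sphericity correction, the F test rejects 7.3% of the time when nothing differs, and the family-wise error of that procedure is 6.4%. Ungated Holm stays at 3.8% to 4.2% under that pattern.

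**The case against.** The strongest reply is that an ANOVA followed by Bonferroni is a standard, valid and conservative procedure, and that choosing another is a matter of taste for a comparison with no stated primary status. Validity and low stakes stand. The appeal to taste does not: on the same pairwise p-values, Holm declares everything the plan declares at the same family-wise level.

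A reader might infer more than the documents support:

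- **That the gate itself is a heavy penalty.** With equal SDs it costs about 1 point or less per pair; most of the avoidable loss is single-step Bonferroni. A large gate cost appears only in an assumed extreme pattern: SDs 1:1:3 with the effect confined to a low-variance measure, where power for at least one pair at n=86 falls from 80% to 24%. With the effect in the high-variance measure the cost is about 0.1 point. The documents give no SDs, so they neither show nor exclude such a pattern.
- **That the gate buys no error control at all.** It does lower the error when nothing differs, from 4.4% to 3.9% at n=86. The gain is not needed.
- **That the usable n is well below 86.** The error-only definitions make this plausible, but no error counts are given. If it is so, the selection of subjects who made both kinds of error is a separate problem that no multiplicity method repairs.

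The section is also written in the past tense, so the analysis may already be done. That affects how a change is labelled, not whether it is sound.

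**Conclusion.** The point holds as a minor improvement. The planned procedure is valid, and no conclusion reached with it is put in doubt. It is needlessly conservative: ungated Holm keeps every pair the plan would declare, holds family-wise error at 5%, and adds about 4 points of power per truly different pair where power is not already near 100%.

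The dominance result is a matter of logic, given the same pairwise p-values. The size rests on assumed normality, equal SDs, correlation 0.5, the chosen shifts and n from 20 to 86. The gain lies in declaring further pairs. For finding at least one pair Holm equals ungated Bonferroni, because its first step is the same, so that gain is only what dropping the gate gives: 0.4 to 1.2 points at n=86 and 0.8 to 2.3 at n=20 with equal SDs.

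**What to change.** In the last sentence of the Statistical analysis Plan, replace the ANOVA followed by conditional Bonferroni tests with paired comparisons of CT-RTs, RTs total and RT misses, Holm-adjusted over the three pairs at family-wise 5% and not conditional on the ANOVA. The ANOVA may still be reported descriptively. State the pairwise statistic and report how many subjects have all three values. If results have already been seen, label the change as a revision and show the original analysis beside it.

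Do not substitute the ANOVA gate with unadjusted 0.05 tests: that needs an omnibus test that remains valid without sphericity, which the plan does not specify.

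The cost is one sentence and no new data. There are two small downsides: the error when nothing differs rises slightly (3.9% to 4.4% at n=86) but stays below 5%, and Holm gives no simple simultaneous confidence intervals.
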